- Although a significant number of patients with advanced operable breast cancer achieve pathological complete response (pCR) after treatment with a combination of primary chemotherapy and targeted therapy, not much is known whether surgical resection improves the risk of local recurrence after pCR. pCR is defined as the absence of any residual tumor in the final biopsy results after neoadjuvant chemotherapy.
- Previous studies in patients with breast cancer showed a relatively high local recurrence rate after clinical response was achieved with neoadjuvant radiotherapy.
- Thus, there is a need to develop an accurate prediction method for pCR before the surgery and a method to accurately identify and screen patient groups requiring local resection despite achieving pCR.
- Also, the local recurrence rate was high in patients who did not undergo surgery once they achieved clinical complete response. However, there was no difference in overall survival. Most local recurrences in patients with breast cancer were observed during regular follow-up visits, thus making treatment easier and preventing systemic metastasis of the disease. In addition, the fact that the recurrence rate differed significantly according to the presence of suspected tumor on ultrasound examination, along with clinical observation, also suggests that it is possible to omit surgical treatment when accompanied by accurate preoperative evaluation.
- In other words, it is of critical importance to accurately determine the pCR through the use of advanced breast imaging techniques after neoadjuvant chemotherapy is completed, which in turn can provide important clues for determining future treatment options.
- Advances in anticancer drugs and targeted therapies and a continued development of combination therapies have led to an increase in pathological responses to values as high as 40-67% after neoadjuvant chemotherapy. The results from this study are expected to contribute to making decisions for de-escalation of treatment for an increased number of patients.

2) Study Hypothesis and Purpose

- A. To develop a non-surgical and accurate method to determine the pCR after neoadjuvant chemotherapy.
 - Accurate prediction of pCR is important for safe omission of surgery in patients deemed to have achieved complete response after neoadjuvant chemotherapy.

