 - In a previous study, sensitivity to residual tumors after neoadjuvant chemotherapy was measured using breast MRI was at 83%, specificity 47%, positive-predictive value (PPV) 47%, negative-predictive value (NPV) 83%, and accuracy 74%.
 - Histological examination of tumors is considered to be an important factor in improving accuracy. The accuracy of pCR prediction is determined to be acceptable when it is 90% or higher, considering that local recurrence rate is about 10% in patients undergoing surgical resection, as observed in previous studies.
 - In this study, pCR prediction results of breast magnetic resonance imaging (MRI) and biopsy (multiple-core needle biopsy and vacuum-assisted breast biopsy) will be compared with the prediction results of the breast specimens undergoing quadrantectomy involving primary tumors.
 - If residual tumors are observed in the surgical specimens, pathological factors such as the distance from the primary tumor with clipping and the occurrence of necrosis will be analyzed.
- B. To develop a basic examination technique that would allow screening of patients based on whether they need local resection or not, when making preoperative determination by pathological response.
 - The pCR after neoadjuvant chemotherapy will be determined by non-surgical method.
 - Using a RCT design, enrolled patients will be divided into two groups based on whether they received

- surgery or not.
- Follow-up with local recurrence rate will be the primary endpoint, while disease-free survival (DFS) and overall survival (OS) will be the secondary endpoints. Based on the results, patients who do not need surgical treatment will be identified.
- In this study, if the pCR can be accurately determined, it is possible to conduct further studies on the extent of surgery (local excisional biopsy with local anesthesia vs. multiple-core needle biopsy vs. segmentectomy)

3. Investigational product and medical device code name (or common name of main ingredient), amount of drug substance, formulation, etc. (including a control drug)

Not applicable.

4. Selection Criteria, Exclusion Criteria, Target Number of Patients and Basis for Calculation

1) Selection Criteria

All patients undergoing neoadjuvant chemotherapy and those who are expected to have near complete or complete clinical response immediately before surgery, as confirmed by MRI will be included. (tumor size ≤ 0.5 cm or Lesion-to-Background Signal Enhancement Ratio [L-to-B SER] ≤ 1.6).

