2) Exclusion Criteria

- Multifocality (≥ 3)
- Residual diffuse microcalcification
- Patients who drop out due to complications or cancer progression during neoadjuvant chemotherapy.
- Patients with residual tumors observed immediately before surgery, as observed by MRI and ultrasound.

3) Target number of patients and basis of calculation

The primary endpoint of this study is to perform an additional biopsy after MRI to determine if specificity was greater than 90% (one-sided test). To calculate the number of patients to meet this primary endpoint, the following assumptions were made.

※ Gold standard: biopsy after surgery

- (1) Level of significance, $\alpha = 0.05$, one-sided test
- (2) Type II error (β) is 0.20, and the test power is maintained at 80%.
- (3) The hypothesis of this study is as follows.

Null hypothesis: The specificity of MRI + biopsy is not 64% ($p \neq 0.64$).

Alternative hypothesis: The specificity of MRI + biopsy is greater than 64% ($p > 0.64$). However, a specificity of 90% is expected.

(4) Based on the results from previous studies, MRI data showed that 64% of the patients had no tumors in the actual surgical tissues. Therefore, the specificity of MRI is assumed to be 64%. In case of MRI + biopsy, specificity is expected to be 90%.

Based on this, the number of study patients was calculated using the below formula.

$$n = \frac{(z_\alpha \sqrt{p_0 q_0} + z_\beta \sqrt{p_1 q_1})^2}{\delta^2}$$

Based on the calculation, 17 patients are required to secure 80% probability of rejecting the above null hypothesis at a significance level of 5%.

At this time, 17 patients were counted using the specificity (ratio of complete response in the MRI + needle biopsy results from the patients who would show complete response in the biopsy after surgery [gold standard] results), so it would only represent the number of patients who would have complete response as a result of biopsy after surgery. Therefore, the total number of patients should be calculated by reflecting prevalence (among 100 patients suspected of complete response in our study, the ratio of actual complete response in the postoperative biopsy is 64%) and the results are as follows.

Prevalence (A)	Total number of patients (B)	Number of total study patients considering the dropout rate 10% (C)
64%	27	30

4) Study Patient Recruitment Plan

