Based on the above calculations, a total of 30 patients would be sufficient for this study. However, an additional 10 patients were included for further analysis to compare multiple-core needle biopsy and vacuum-assisted breast biopsy, thereby allowing 20 patients in each group.

Among the patients who were admitted for surgery after neoadjuvant chemotherapy (admitted 2 days before surgery), those who were expected to have a complete response immediately before surgery, based on the MRI and ultrasound results, will be given an explanation with regard to study plan, etc.

5. Study Method

1) Detailed study method

A. Breast MRI for assessing response after neoadjuvant chemotherapy

- Breast MRI diagnosis will be interpreted independently of clinical measurements, mammography, and breast ultrasonography results.
- Two breast MRIs will be done for patients who have received neoadjuvant chemotherapy, one before and one after the therapy.
- The images obtained before and after chemotherapy will be examined by a breast diagnostic imaging specialist to assess the exact response of the tumor to neoadjuvant chemotherapy and the presence of residual tumor.
- A complete MRI response means no abnormal contrast enhancement, no mass, or no distortion of the breast tissue in all phases of the MRI and in all compartments of the breast.
- A near complete MRI response means tumor size ≤ 0.5 cm or Lesion-to-Background Signal Enhancement Ratio [L-to-B SER] ≤ 1.6 .
- The response will be evaluated based on the results of breast ultrasonography and mammography, in addition to breast MRI. In case of residual tumor findings, such as clustered microcalcification on mammography, the patient will be excluded even when an abnormal contrast enhancement is not observed.

B. Biopsy in patients whose complete response is predicted by breast MRI

- In previous studies, attempts to predict the complete response using diagnostic images of breast alone showed about 21% false negative findings. Additional confirmation of pCR using multiple-core needle biopsy or vacuum-assisted breast biopsy can lower such false negative findings.
- A needle biopsy or vacuum-assisted breast biopsy will be performed around the residual tumor and the periphery and a wire will be inserted for localization of the biopsied area. The wire will guided the subsequent wide excision.

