4. Reporting procedures to the IRB, sponsor and, where applicable, the regulatory agency (description on the reporting method and period to the IRB, sponsor, or regulatory on adverse events, unexpected problems, non-compliance with the protocol, etc.)

: Problems encountered during the study will be discussed with the principal investigator, [name] and will also be reported to the IRB office.

9) Data Analysis and Statistical Analysis Method

The results from the preoperative MRI and biopsies (multiple-core needle biopsy and vacuum-assisted breast biopsy) and postoperative pathology will be compared to examine the accuracy of the prediction of complete response or residual tumor.

Primary Endpoint

- Negative-predictive value (NPV)

Secondary Endpoint

- False negative rate (FNR)
- Accuracy
- NPV, FNR, and accuracy analysis for cases meeting all the conditions of MRI size ≤ 0.5 cm, L-to-B SER ≤ 1.6 , and removal of multiple-core needle biopsy 5 core or more

In addition, the patients will be divided equally into the multiple-core needle biopsy group and the vacuum-assisted breast biopsy group to determine which biopsy method could predict the complete response more accurately.

6. Measures for the Protection of Patients

1) Basic measures for securing research ethics

This study will be initiated after receiving IRB approval and conducted in compliance with the 2013 Helsinki Declaration and ICH-GCP

2) Measures to protect personal information of patients

Patients' information, collected for study purpose, will be stored in the laboratory as password-protected files. Access to these files will be restricted to the principal investigator and co-investigators. Personally identifiable information, acquired during data collection, will not be recorded. Especially, patient's name, national resident number, and hospital registration number will not be documented in the case record.

When the results of the study are published, no identification data of the patients will be provided and the case records will be kept separately with the principal investigator, until the final publication of the results after study termination. The data and records will be retained for three years after the termination of the study. Subsequently, these will be discarded under the direction of the principal investigator in accordance with the Article 16 of the Enforcement Decree of the Personal Information Protection Act.

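### Section 4.3 tests and powers specificity, Section 5.9 makes NPV primary with no null, test or power, and the 64% null called MRI specificity is a predictive value

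*Combined protocol and SAP*

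**What the plan says.** Section 4.3 of the protocol (target number of patients) states: "The primary endpoint of this study is to perform an additional biopsy after MRI to determine if specificity was greater than 90" percent. It sets a one-sided 5% level, 80% power, a null value of 64% and an expected value of 90%, and arrives at 17, then 27, then 30 patients. It describes the specificity it counts as the "ratio of complete response in the MRI + needle biopsy results from the patients who would show complete response in the biopsy after surgery", so the denominator is patients with complete response at surgery.

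Section 5.9 (statistical analysis) names a different primary endpoint (the entry is "Negative-predictive value (NPV"). False negative rate (FNR) and accuracy are secondary. Specificity does not appear, and no null, test, level or power is given for NPV.

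On the null value, Section 4.3 says "Therefore, the specificity of MRI is assumed to be 64" percent. A few lines later it uses the same figure as a prevalence: "among 100 patients suspected of complete response in our study, the ratio of actual complete response in the postoperative biopsy is 64" percent.

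Section 2.2 A gives the purpose: "Accurate prediction of pCR is important for safe omission of surgery in patients deemed to have achieved complete response". The same section calls pCR prediction acceptable at 90% or more, and states that level for accuracy.

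**The concern.** Specificity and NPV answer different questions. Specificity asks how often the test is negative in patients who have pCR. NPV asks how often a patient with a negative test really has pCR. Leaving out surgery safely depends on the second question and on how often tumour is missed. A specificity test carries no information on missed tumour, because patients with residual disease are not in its denominator.

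As written, all the formal inference belongs to an endpoint that the analysis section does not list, and the endpoint it does list has no success criterion. Success could be claimed on either measure once the data are seen. The mislabelled null makes this worse, because an NPV from imaging is being used as the benchmark for a specificity. The section also states an aim of exceeding 90% but tests against 64%.

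**Working it through.** **1. The plan's own figure.** Inputs from Section 4.3: p0 = 0.64, p1 = 0.90, δ = 0.26, one-sided α = 0.05, power 80%.

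n = (z_α√(p0q0) + z_β√(p1q1))² / δ² = (1.645 × 0.48 + 0.842 × 0.30)² / 0.26² = 16.06, rounded up to 17. Then 17/0.64 = 26.6, rounded up to 27, and 27/0.9 = 30. All three figures reproduce as a specificity calculation.

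**2. What the 64% is.** Take residual tumour as the positive result.

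| Quantity | Denominator | Counted |
|---|---|---|
| Specificity, as Section 4.3 defines it | pCR at surgery | test shows complete response |
| NPV | test shows complete response | pCR at surgery |
| The 64% in the prevalence sentence | suspected complete response | pCR at surgery |

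The third row matches the second. Also, only MRI complete or near-complete responders are enrolled. If they count as MRI-negative, the specificity of MRI alone in this cohort is 100% by construction, and adding biopsy cannot raise it from 64%.

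**3. The specificity test.** Basis: 40 less the plan's 10% dropout = 36 evaluable, pCR rate 0.64, and the biopsy decides the combined result. The number with pCR is Bin(36, 0.64). An exact one-sided 5% test against 0.64 at true specificity 0.9, averaged over that number, has power 0.883. Sensitivity does not enter.

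Limiting case, at the plan's own 17 pCR patients: a biopsy that never finds tumour scores 17/17, p = 0.64^17 = 0.0005, with NPV 64% and FNR 100%.

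**4. An NPV test against 64%.** The documents give no biopsy sensitivity, so a range is assumed.

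- Probability of a negative test: q = 0.64·spec + 0.36·(1 − sens)
- NPV = 0.64·spec / q
- Accuracy = 0.64·spec + 0.36·sens
- Test-negatives are Bin(36, q); exact power is averaged over that count

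| Assumed sensitivity (specificity 0.9) | NPV | Accuracy | Specificity test significant | NPV test power |
|---|---|---|---|---|
| 0.5 | 76% | 76% | 88% | 30% |
| 0.6 | 80% | 79% | 88% | 46% |
| 0.7 | 84% | 83% | 88% | 66% |
| 0.8 | 89% | 86% | 88% | 85% |
| 0.9 | 94% | 90% | 88% | 97% |

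At specificity 0.8, NPV test power is 34%, 53%, 75% and 93% for sensitivity 0.6 to 0.9. Reaching 80% power needs sensitivity of about 0.72, 0.77, 0.82 and 0.88 at specificity 1.0, 0.9, 0.8 and 0.7.

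**5. Size in test-negatives.** With 19 test-negatives the exact test rejects at 16 or more correct (size 0.0495), with power 0.885 at true NPV 0.90. For every n from 19 to 40, power at that NPV is at least 0.828. With 36 evaluable and true NPV 0.90, q = 0.64·spec/0.90, which is 0.711, 0.640, 0.569 and 0.498 at specificity 1.0, 0.9, 0.8 and 0.7. The chance of at least 19 test-negatives is then 99%, 94%, 75% and 42%.

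**6. NPV above 90%.** 0.9^28 = 0.052 and 0.9^29 = 0.047, so the smallest result that excludes 90% is 29 of 29 correct. Assuming pCR 64% and specificity 1.0, the chance of a significant result at true NPV 0.95, 0.98 and 1.0 is 1.3%, 2.0% and 2.5% with 36 evaluable, and 6%, 12% and 17% with all 40.

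**The case against.** The strongest reply is that little turns on this in practice. Every participant still has wide excision, so nobody forgoes surgery on the result. Section 5.9 would report NPV and FNR, so a poor biopsy would be visible. The 90% accuracy level in Section 2.2 A would flag it too: accuracy is 76% at sensitivity 0.5 and specificity 0.9, and 64% for a biopsy that never finds tumour. All of this stands. But the accuracy level is a descriptive benchmark with no test attached, and it is not stated for NPV. It does not supply the missing hypothesis.

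A reader might infer three stronger things that the documents do not support.

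- *The trial is too small.* Not shown. By the plan's formula, NPV of 64% against 90% also needs 17, counted as test-negatives, and 40 enrolled gives 85% power at sensitivity 0.8 and specificity 0.9.
- *64% is the wrong benchmark and a higher one must be used.* Section 2.2 A cites an MRI study with "specificity 47%, positive-predictive value (PPV) 47%, negative-predictive value (NPV) 83%, and accuracy 74" percent, and Section 5.1 B says "attempts to predict the complete response using diagnostic images of breast alone showed about 21% false negative findings". The first is not stated to use this trial's eligibility, which admits near-complete responders. The second may be a true false negative rate, in which case its complement is not an NPV. Section 4.3 ties its 64% to patients suspected of complete response in this study. The choice needs a sentence of justification, but neither figure displaces 64%.
- *Forty patients could never show NPV above 90%.* The chance is low but not nil. Near-complete evaluability is plausible, because patients are approached at admission two days before surgery and biopsied when the wire is placed.

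**Conclusion.** The concern holds. Current text in two sections names two different primary endpoints, and the stated level, power and sample size do not apply to the one in the analysis section. The 64% null is a predictive value by Section 4.3's own description, and it is used there as both specificity and prevalence. The contradiction and the mislabel rest on the text alone.

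The size of the consequence depends on assumptions: 36 evaluable, 64% pCR, specificity 0.9, and a biopsy sensitivity that the documents do not give. On that basis the specificity test succeeds 88% of the time throughout, while NPV test power ranges from 30% to 97%. The two diverge most where the biopsy misses most tumour. A formal claim of NPV above 90% is out of realistic reach: about 1% to 3% with 36 evaluable and 6% to 17% with 40, for true NPV 0.95 to 1.0. This must be settled before analysis, although it need not change the number enrolled.

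**What to change.** - Name NPV as the single primary endpoint in Sections 4.3 and 5.9, and make specificity secondary.
- Relabel 64% as the NPV of imaging alone, and delete the sentence that assumes it as the specificity of MRI. Add one sentence on why 64% is the comparator rather than the 83% in Section 2.2 A.
- State H0: NPV ≤ 64% against H1: NPV > 64% (90% expected), with a one-sided 5% exact binomial test among test-negative patients. This also replaces the printed null, which says that the value is not 64%.
- Keep 40 enrolled. Replace the single power figure with a table over assumed biopsy sensitivity and specificity. State that at 36 evaluable and specificity 0.9, 80% power needs sensitivity of about 0.77. Give the 19 test-negatives for 88% power at true NPV 0.90, with the chance of reaching that number.
- Replace the aim of exceeding 90% with a conclusion limited to improvement over imaging alone, and report NPV with its exact confidence interval. Say whether the 90% level in Section 2.2 A, stated for accuracy, also applies to NPV.

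The cost is wording plus a justified choice of comparator. With 64% kept, no patients are added. The downside is a less ambitious claim and a power figure that openly depends on an assumed sensitivity.

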<Study Protocol>

**Prediction of pathologic complete response (pCR) by
preoperative biopsy in breast cancer with complete
clinical response (cCR) after neoadjuvant chemotherapy**

Version No: 3.0

(English version of Korean version approved by IRB on August 12, 2016)

Principal investigator:

[name], MD, PhD

Department of Surgery, Seoul National University Hospital

Department of Surgery, Seoul National University College of Medicine

Cancer Research Institute, Seoul National University

Study Overview

(※ Please provide a clear and concise description of each of the following sections in plain terms that can be understood by non-experts.)

Study Title	(Korean) 선행항암요법을 시행한 유방암 환자에서 유방자기공명영상 및 중심침생검 또는 맘모톰조직생검에 의한 병리학적 완전 관해 예측의 정확도에 대한 전향적 연구 (English) Prediction of pathologic complete response (pCR) by preoperative biopsy in breast cancer with complete clinical response (cCR) after neoadjuvant chemotherapy
Principal Investigator	[name] Department of Breast Endocrine Surgery, Seoul National University Hospital
Study Sponsor Institution	Seoul National University Hospital

Study Purpose	
 ● To develop a non-surgical and accurate method to determine the pathological complete response (pCR) in patients with breast cancer after neoadjuvant chemotherapy. ● To develop a basic examination technique that would allow screening of patients based on whether they need local resection or not, when making preoperative determination by pathological response.
Study Design	
 ● This is a prospective clinical trial. ● Patients with breast cancer, who underwent neoadjuvant chemotherapy and whose diagnostic imaging results, including breast magnetic resonance imaging (MRI), showed near complete or complete clinical response (i.e., no residual tumor) will be enrolled. ● On the day before the surgery or on the day of surgery, needle biopsy or vacuum-assisted biopsy will be performed in the eligible patients, focusing on the primary tumor and the peripheral area. The biopsied area will be localized with a wire. Wide excision will be performed subsequently. ● Accuracy of the prediction of pCR by breast MRI and multiple-core needle biopsy or vacuum-assisted breast biopsy will be determined by analysis of final pathological findings of the surgically removed breast tissue.
Study Period	August 12, 2016 ~ August 11, 2018

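### The reference is the surgical specimen alone, so carcinoma found in the pre-operative cores but absent from the specimen counts as a false positive; NPV is not affected, accuracy, specificity and FNR are

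*Combined protocol and SAP*

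**What the plan says.** Section 4.3 states "Gold standard: biopsy after surgery". It defines specificity as the "ratio of complete response in the MRI + needle biopsy results from the patients who would show complete response in the biopsy after surgery", so every patient with a clean specimen is in the denominator.

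The Study Design entry of the overview says that the accuracy of MRI plus biopsy "will be determined by analysis of final pathological findings of the surgically removed breast tissue". Sections 5.5 and 5.9 make the same comparison, with the final or postoperative pathology. Section 5.5 puts atypical cells, DCIS and invasive ductal cancer together in the residual tumor group.

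The index biopsy comes before the specimen: "On the day before the surgery or on the day of surgery, needle biopsy or vacuum-assisted biopsy will be performed" (Study Design). Section 5.1 B uses a 14-gauge core needle or a 10-gauge vacuum device, recommends at least five cores, and says that "vacuum-assisted breast biopsy will be performed around the residual tumor and the periphery". Entry requires "tumor size ≤ 0.5 cm or Lesion-to-Background Signal Enhancement Ratio [L-to-B SER] ≤ 1.6" (section 4.1).

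Section 5.9 names NPV as the primary endpoint and FNR and accuracy as secondary, and plans a comparison of the two biopsy methods. Section 4.3 calls specificity the primary endpoint and sizes the study on it. No section says how to score a patient with carcinoma in the cores and a clean specimen.

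**The concern.** The index test removes tissue from the place that the reference then examines. If the cores take out the last of the carcinoma, the biopsy was right that disease remained after chemotherapy, yet the specimen is clean and the stated rule records an error. A correct positive becomes a false positive.

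Accuracy, specificity and FNR can be affected. The comparison of biopsy methods is the most sensitive. The two devices differ in gauge, so the number of such patients could differ between arms, and a device that removes more of the residue could look less accurate for that reason. With no rule in the plan, the scoring could also be settled after the results are known.

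**Working it through.** **The plan's own figures.** Section 4.3 gives one-sided α = 0.05, power 80%, p0 = 0.64, p1 = 0.90.

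n = (1.6449 × √(0.64 × 0.36) + 0.8416 × √(0.90 × 0.10))² / 0.26² = (0.7896 + 0.2525)² / 0.0676 = 16.06, rounded up to 17. Then 17 / 0.64 = 26.6, rounded up to 27, and 27 / 0.9 = 30. The stated 17, 27 and 30 reproduce. They are not in dispute.

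**Effect of the scoring rule.** Let k be the number of patients with carcinoma in the cores and a clean specimen. Take TP, FP, FN and TN as the counts when these patients are true positives. The specimen-only rule moves k from TP to FP:

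| Measure | Core-proven carcinoma counted as disease | Specimen alone | Change |
|---|---|---|---|
| Accuracy | (TP + TN) / N | (TP + TN − k) / N | falls by k/N |
| Specificity | TN / (TN + FP) | TN / (TN + FP + k) | falls |
| FNR | FN / (FN + TP) | FN / (FN + TP − k) | rises only if FN > 0 |
| NPV | TN / (TN + FN) | TN / (TN + FN) | none |

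Section 5.9 gives no formula for FNR; the usual FN / (FN + TP) is assumed.

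**Assumed numbers.** 40 planned less the 10% dropout of section 4.3 leaves 36, or 18 per arm. 64% of 36 is 23 tumour-free, leaving 13 with residual disease. The value of k is unknown, so effects are per patient.

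- Accuracy: 1/36 = 2.8 points overall; 1/18 = 5.6 points in one arm.
- FNR, going from k = 0 to k = 1: with 1 missed, 1/13 = 7.7% becomes 1/12 = 8.3% (+0.6 points); with 3 missed, 23.1% becomes 25.0% (+1.9); with 5 missed, 38.5% becomes 41.7% (+3.2); with none missed, no change. For scale, the exact 95% interval for 3/13 is 5% to 54%.
- NPV: no change.

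**Specificity, as an illustration.** Assume no other false positive and an exact one-sided binomial test against 64%. The answer depends on what the 64% means.

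- If 64% is the specimen-clean rate, as section 4.3 words it, 23 is a fixed denominator. With k = 4, 19/23 = 82.6%, p = 0.045; with k = 5, 18/23 = 78.3%, p = 0.111. The test is lost at five.
- If 64% is the rate before any coring, the denominator is 23 + k. With k = 5, 23/28 = 82.1%, p = 0.031; with k = 6, 23/29 = 79.3%, p = 0.060. The test is lost at six, when 29/36 = 81% of specimens would be clean.

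**The case against.** **The main result is untouched.** This stands. NPV uses biopsy-negative patients only. A reader might infer that the reference inflates the case for omitting surgery. It does not: the affected patients are biopsy-positive, and the error makes the biopsy look worse.

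**The expected specificity already allows for these patients.** A reader might put them on top of an expected result of about 90%, say 21/23, and conclude that three would lose the test (21/26, p = 0.053). The documents do not support that. Section 4.3 sets the 90% against the post-surgical reference, so its allowance for false positives already includes any core-positive, specimen-clean patient. Adding them again counts them twice.

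**The 90% level may not concern overall accuracy.** Section 2.2 A says "The accuracy of pCR prediction is determined to be acceptable when it is 90% or higher" and justifies it by a local recurrence rate of about 10% after resection. That fits residual tumour among patients predicted to be clear (1 − NPV) at least as well. A reader might count how few errors use up a 10% margin, but the text does not establish that this margin applies. It is a possible benchmark only.

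**Complete removal may be rare.** The entry rule joins size and enhancement ratio with *or*, so lesions above 0.5 cm can enter. Section 4.2 excludes residual tumours seen on MRI and ultrasound, and section 5.1 B spreads the core-needle samples over five locations. Removal of the whole residue is possible; nothing shows it to be common, and the effect could be zero.

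**The specimen is the plan's stated target, and the alternative is biased too.** This is fair. If carcinoma in the cores counts as disease, a carcinoma-positive core can never be wrong. That argues for showing both references, not for replacing one. Nor does every section name surgical tissue: the definition of pCR in section 2.1 refers only to final biopsy results after chemotherapy, and the point does not rest on it.

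**Conclusion.** The point holds as a limited one. Under the rule stated in the Study Design entry and sections 4.3, 5.5 and 5.9, core-proven DCIS or invasive carcinoma with a clean specimen is a false positive. Accuracy and specificity fall, FNR rises when at least one tumour is missed, and NPV is unchanged.

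The frequency is not in the documents, so no total bias can be given. The per-patient sizes rest on 36 evaluable patients, equal arms and 13 with residual disease. The FNR effect is negligible at this sample size. The 5.6 points per patient within an arm are the main reason to act, because the count could differ between the 14-gauge and 10-gauge methods. The specificity illustration shows only that five or six such patients, with no other false positive, would be needed to lose the test. Cheap improvement.

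**What to change.** In sections 5.5 and 5.9, pre-specify that accuracy, FNR and the comparison of biopsy methods are reported under two references:

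1. the surgical specimen alone;
2. the specimen, or carcinoma (invasive or DCIS) in the pre-operative cores.

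Under reference 2, a patient with carcinoma in the cores and a clean specimen is a true positive. A patient with atypia-only cores and a clean specimen stays a false positive under both. State the FNR formula. List all core-positive, specimen-clean patients by biopsy method and histology.

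Leave the calculation in section 4.3 as it is. Keep the specificity test against 64% on the specimen alone, label it so, and note that core-proven carcinoma with a clean specimen counts against it.

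The cost is a few sentences, one listing and one extra 2×2 table; both pathology results are already collected. The downside is incorporation bias: reference 2 contains the index test and so favours it. The two results should therefore stand side by side, with reference 2 as a sensitivity analysis.
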